MU Health
EM Research Working Group
Project Proposal

Administrative Summary

Project Title	Methylnaltrexone versus Naloxegol in the Treatment of Opioid-Induced Constipation in the Emergency Department
Primary Investigator	[name], BCPS
Others Involved	[name]; [name]; [name]
Estimated Budget	Methylnaltrexone oral tablet - \$17.07 per tablet Methylnaltrexone 12mg subcutaneous injection - \$93.96 Naloxegol 25mg oral tablet - \$9.14 per tablet

For 20 doses of each medication:

\$51.21 x 20 = \$1,024.20

\$93.96 x 20 = \$1,879.20

\$9.14 x 20 = \$182.80

Total: \$3,086.20

Funding Source	Missouri College of Emergency Physicians
Protocol Version	v2
Protocol Date	04/18/2023
Special Considerations	None

Project Overview

Background / Significance:

Opioid-induced constipation can lead to serious complications, including small bowel obstruction, fecal impaction, and bowel perforation.¹ Not only are the medical complications potentially severe, patient quality of life can also be impacted.² Two agents are currently available for opioid-induced constipation – oral and subcutaneous methylnaltrexone and oral naloxegol. Mechanistically, both agents antagonize the

peripheral mu-opioid receptor in the gastrointestinal tract to decrease constipation without reversing the systemic analgesic effects of opiates.³ The literature currently available has evaluated the effectiveness of each agent, not the comparative effectiveness of these agents.

Purpose / Study Aims:

The purpose of this study is to compare the efficacy of subcutaneous versus oral mu-opioid receptor antagonist therapy in opioid induced constipation that is refractory to other bowel regimens.

Primary Outcome: The primary outcome of this study is to determine the effectiveness of peripherally acting mu-opioid receptor antagonist therapy for patients presenting to the emergency department (ED) with opioid-induced constipation.

Secondary Outcomes: The secondary outcome of this study is the time to effectiveness of subcutaneous versus oral therapy.

Feasibility (sample size, frequency of eligible patients, duration of study):

Sample size: 15 patients (due to changes in standard of care procedures the enrollment goal had to be reduced)

Duration: 2 years

Study Procedure

1. Methods
 - a. Patients presenting to the Emergency Department with opioid induced constipation will be screened for inclusion in one of three groups:
 - i. Methylnaltrexone oral tablets (total 450 mg)
 - ii. Methylnaltrexone 12mg subcutaneous injection
 - iii. Naloxegol oral tablets (total 25 mg)
 - b. A pregnancy test will be administered to females of childbearing potential before administration of the study drug.
 - c. After treatment patients will
 - i. Have a successful bowel movement, thus completing their time in the study to continue with standard patient care
 - ii. Not have a successful bowel movement after 3 hours, continue with standard patient care, and be contacted in 24 hours to record the time of any successful bowel movements after the 3 hours study period

2. Data collected

- a. Age
- b. Sex
- c. Current medications
- d. History of constipation
- e. Time of last bowel movement
- f. Attempts to alleviate current constipation
- g. Time to successful bowel movement after treatment
- h. Phone number or other contact information
- i. Side effects noted by patient or staff

3. Subjects

- a. Inclusion criteria
 - i. Complaint of opioid-induced constipation refractory to other therapy (enemas, laxatives, stool softeners)
 - ii. Age \geq 18y/o
 - iii. Not pregnant or lactating (negative urinary pregnancy test)
 - iv. No contraindication to Methylnaltrexone or Naloxegol
- b. Exclusion criteria
 - i. Age $<$ 18y/o
 - ii. Pregnancy or lactation
 - iii. Contraindication to Methylnaltrexone or Naloxegol
 - iv. Assigned NPO
 - v. Small bowel obstruction

4. Treatment of subjects

- a. If the subjects are eligible for inclusion they will be offered inclusion in the study by one of the Emergency Department faculty. If they refuse participation they will be treated in a standard fashion.
Patient follow-up will cease after 24 hours
- b. Benefits
 - i. Patient benefits: patient may achieve relief from opioid-induced constipation
 - ii. Society benefits: To our knowledge, this is the first time these two drugs are being compared for their efficacy
- c. Risks: *Allergic reaction, stomach/abdominal pain, gas, nausea, diarrhea, dizziness, increased sweating, hot flashes, flushing, tremor, chills, black or bloody stools, coughing up blood*
- d. Compensation: The patients will not be compensated for study inclusion

5. References

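### Treatment given after the study dose is not recorded, so a bowel movement at 3 to 24 hours cannot be attributed to the study drug or to later care

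*Protocol*

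**What the plan says.** Study Procedure 1.c of the Protocol gives two paths after dosing. On the first, patients will "Have a successful bowel movement, thus completing their time in the study to continue with standard patient care". On the second, they will "Not have a successful bowel movement after 3 hours, continue with standard patient care, and be contacted in 24 hours to record the time". The events to be timed at that contact are "any successful bowel movements after the 3 hours study period". Follow-up ends at 24 hours (section 4.a).

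The only outcome time in section 2 is item 2.g, "Time to successful bowel movement after treatment". It carries no 3-hour cut-off and no rule for treatment given in between. The two items that touch on treatment are 2.c, "Current medications", and 2.f, "Attempts to alleviate current constipation". Neither is timed. Both come before 2.g, among the history items.

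The primary outcome is to "determine the effectiveness of peripherally acting mu-opioid receptor antagonist therapy for patients presenting to the emergency department" with opioid-induced constipation. The secondary outcome is the time to effect of subcutaneous against oral therapy. No success criterion or time point is given for either. The SAP states 1:1:1 randomisation and descriptive statistics only. It defines no endpoint and does not say how treatment given after the dose is handled.

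**The concern.** The Protocol collects movement times well beyond the point at which patients go on to other care, but does not collect what that care was. A movement at, say, 10 hours may be a late effect of the study drug or the effect of something given at 4 hours. With the listed items the two look identical.

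The problem is not symmetric between arms. Only patients without a movement at 3 hours take this path, so the arm with fewer early responders sends more patients to further care and has more to gain if later movements count. There is no untreated arm and no test is planned, so the per-arm or per-route counts and times are what a reader will compare. No error rate is at stake; the meaning of the descriptive results is.

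An undefined endpoint can still be settled when the report is written. Treatment data that were never gathered cannot be filled in then, except where another record happens to hold them.

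**Working it through.** **Plan figures.** The documents give no figure on this point. The one design number that can be rebuilt is the SAP's original total: 14 x 3 = 42, and 42 + 18 = 60, which equals 20 x 3. The argument does not depend on it. The Protocol's reduced target is 15 patients; at the SAP's 1:1:1 allocation that is 15 / 3 = 5 per arm. One reclassified patient moves an arm by 1/5 = 20 percentage points. If the two oral arms are pooled for the route comparison, one patient moves the pooled group by 1/10 = 10 points.

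**What each data item can show.**
- 2.c and 2.f: untimed and placed with the history. On the natural reading they describe the patient before dosing.
- 2.g: when the movement occurred, not what came before it.
- 2.i: side effects.
- 2.a, 2.b, 2.d, 2.e and 2.h: age, sex, constipation history, last movement and contact details.
- 24-hour contact: its only stated purpose is the time of the movement.

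No item identifies treatment between the dose and the movement.

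**Effect if 24-hour movements count.** Let p be the 3-hour response in an arm and r the share of 3-hour non-responders who move because of later care. Assume that r is equal across arms and that every movement after 3 hours is due to later care.

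24-hour response = p + (1 - p)r

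Difference between arms = (p1 - p2)(1 - r)

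Neither p nor r is in the documents; all values below are assumed.

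| r | 80% v 40% at 3 h becomes | Difference | 60% v 30% at 3 h becomes | Difference |
|---|---|---|---|---|
| 0 | 80 v 40 | 40 | 60 v 30 | 30 |
| 0.25 | 85 v 55 | 30 | 70 v 47.5 | 22.5 |
| 0.5 | 90 v 70 | 20 | 80 v 65 | 15 |
| 0.75 | 95 v 85 | 10 | 90 v 82.5 | 7.5 |
| 1 | 100 v 100 | 0 | 100 v 100 | 0 |

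For example, 0.8 + 0.2 x 0.5 = 0.90 and 0.4 + 0.6 x 0.5 = 0.70. In the 60% v 30% case at r = 0.5, later care accounts for 0.20/0.80 = 25% of successes in the better arm and 0.35/0.65 = 54% in the worse arm.

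**Effect if only 3-hour movements count.** Movements after 3 hours do not enter, so the difference stays at p1 - p2 (40 or 30 points here) whatever r is.

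**Time to effect.** Any summary that uses times between 3 and 24 hours is open to the same mixing. One that stops at 3 hours is not affected by later care.

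**The case against.** The strongest reply is that the Protocol calls 3 hours the study period and divides patients by whether they have moved by then. A 3-hour endpoint is a natural reading, and under it the shrinkage in the table disappears. This stands. A reader might infer that later movements are in fact credited to the randomised drug, but no section says so. What is established is that the plan leaves it open.

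A reader might also infer that patients switch to another study drug, since the Background says "Two agents are currently available for opioid-induced constipation", or that other bowel treatment is given within the first 3 hours. The documents neither describe nor exclude either. Both are possibilities that the data list could not detect, not events the plan provides for.

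Further points carry some weight:
- Patients enter because enemas, laxatives or stool softeners have failed, so r may be low. It is unknown, and prior failure does not fix it.
- The formula gives the study drug no late effect. To the extent that it has one, the table overstates the role of later care.
- Items 2.c and 2.f could be stretched to cover later treatment. Their position argues against it, and without times they would not settle the order of events.
- It would be too strong to say the information is lost. Treatment given in the department may be in the chart; treatment taken at home probably is not.
- The SAP is written in the past tense, so a new form field may come too late for some or all patients.
- Counting every movement by 24 hours regardless of later care is a legitimate summary if labelled as such. It then describes an initial drug followed by usual care, not the drug alone.

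**Conclusion.** The point holds as a gap in data collection combined with an undefined effectiveness window. Followed as written, the plan cannot separate study drug from later care for movements at 3 to 24 hours, and nothing prevents those movements from entering the effectiveness result or the time summary.

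The size depends on a choice the documents do not make. If 24-hour movements count, the difference between arms falls by the proportion r, in favour of the weaker arm; an assumed 40-point difference becomes 20 at r = 0.5. If only 3-hour movements count, later care causes no distortion. The first figure rests on assumed response rates, equal r across arms and no late drug effect; if r differs between arms, the simple factor (1 - r) no longer applies.

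The consequence is for interpretation of a small descriptive report. It is worth correcting because the remedy is cheap and what was not recorded may not be recoverable.

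**What to change.** **Data collection (Protocol section 2).** Add one item: type and time of any bowel treatment, opioid antagonist (study drugs included) or opioid given between the study dose and the movement or 24-hour contact. Take it from the emergency department record and one question at the existing contact.

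**Patients already enrolled.** Extract department treatment from the chart, and state unrecorded home treatment as a limitation.

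**Reporting (SAP).** Define the effectiveness result as movement within 3 hours of the study dose, by randomised arm. Flag any such movement preceded by other treatment. List movements at 3 to 24 hours separately, split into those with other treatment first, those without, and those where this is unknown. Apply the same separation to the time summary.

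This changes recording and reporting only, not the care given. The cost is one field, one question and one table column for about 15 patients, plus a chart review where enrolment is complete. The drawbacks are reliance on patient recall for treatment at home and possibly lower reported effectiveness than a 24-hour count would give.

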Study Title: *MethylNaltrexone versus Naloxegol in the Treatment of Opioid-Induced Constipation in the Emergency Department*

NCT number: NCT03523520

Date: 09/04/2024

Statistical analysis plan

Population: Patients with opioid-induced constipation refractory to other bowel regimens.

Feasibility: (sample size, frequency of eligible patients, duration of study):

Sample size: Sample size calculations were performed prior to study initiating resulting in the need for a total of 60 participants (14 in each arm [rounding up to 20 per arm], adding 18 participants to account for dropouts)

Frequency predictions for feasibility: 5 patients per month

Participants randomized in a 1:1:1 pattern assigned by pharmacy staff. Study investigators blinded to randomization and study drug.

Statistical considerations:

Previous statistical plan included frequency analyses by Chi-Square and parametric ANOVA calculations with pairwise comparisons.

Due to local changing prescribing patterns of opioids, the potential participant population was reduced to levels of infeasibility for continuation of this study. Therefore, only descriptive statistics were performed. No conclusive tests were performed.

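### Must the SAP be changed because it omits the reduced goal of 15 and does not name its descriptive summaries?

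*SAP*

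**What the plan says.** The SAP's Feasibility section reports a calculation made before the study started, with a "need for a total of 60 participants (14 in each arm [rounding up to 20 per arm], adding 18 participants to account for dropouts". It then adds "Frequency predictions for feasibility: 5 patients per month". Under Statistical considerations it records what was planned at first: "Previous statistical plan included frequency analyses by Chi-Square and parametric ANOVA calculations with pairwise comparisons". It explains that "the potential participant population was reduced to levels of infeasibility for continuation of this study" and concludes: "Therefore, only descriptive statistics were performed. No conclusive tests were performed".

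Protocol v2, the earlier of the two documents, gives under Feasibility "Sample size: 15 patients (due to changes in standard of care procedures the enrollment goal had to be reduced" and "Duration: 2 years". Its aims remain comparative: "The purpose of this study is to compare the efficacy of subcutaneous versus oral mu-opioid receptor antagonist therapy in opioid induced constipation". The secondary outcome is time to effect, subcutaneous against oral. Under Study Procedure, a patient with no bowel movement in the 3-hour study period is contacted at 24 hours, and follow-up then ends.

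The SAP does not give the goal of 15, the numbers enrolled or analysed per arm, or the particular descriptive summaries.

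**The concern.** Someone reading only the SAP sees 60 patients and 5 per month, and could picture a trial much larger than the one its last paragraph describes. Without denominators, that reader cannot judge how much each arm's summary is worth.

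The time outcome raises a further question. A patient with no bowel movement by the 24-hour contact has no recorded time. If an analyst averaged only the recorded times, non-responders would drop out and the less effective arm could look faster. With no summary named, nothing in the text rules that out. The protocol's comparative purpose also sits awkwardly beside an analysis that tests nothing.

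**Working it through.** **Reproducing the 60.** Inputs from the SAP: three arms allocated 1:1:1, 14 per arm, 18 added.
- 3 × 14 = 42, and 42 + 18 = 60.
- 3 × 20 = 60, so the rounding to 20 per arm is the same allowance stated another way.
- 18/60 = 30% assumed dropout, and 42/(1 − 0.30) = 60.
- The protocol's budget for 20 doses of each medication matches this original size.

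The 14 per arm cannot be rebuilt, because neither document gives alpha, power or an effect size. The point does not depend on it.

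**60 against 15.** The SAP ties 60 to the time before the study. The protocol says its 15 is a reduction. One is the original target and the other the revised one, so they do not conflict.

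**5 per month against the goal of 15.** Inputs: 5 per month (SAP), 2 years and 15 patients (Protocol v2).
- 5 × 24 = 120 patients over two years.
- 15/24 = 0.625 per month, and 5/0.625 = 8.

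The eightfold ratio does not compare like with like. The SAP's line is a prediction, under a heading that concerns how often eligible patients appear, whereas 15 is an enrolment goal. Eligible patients may decline, so the first should exceed the second. The 120 also joins an original prediction to a duration taken from the version with the reduced goal, and the documents do not say whether two years was the original duration.

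**Does the smaller size support dropping the tests?** Assume 15 are reached and split evenly: 15/3 = 5 per arm.
- Exact (Clopper-Pearson) 95% intervals: 3/5 gives 15% to 95%; 8/14, at the original evaluable size, gives 29% to 82%.
- Assume two-sided alpha 0.05 and 80% power (neither is in the documents). The standardised difference detectable with 14 per arm is √(2/14) × (1.96 + 0.84) ≈ 1.06.
- With 5 per arm, power for that difference is Φ(1.06/√(2/5) − 1.96) ≈ Φ(−0.29) ≈ 39%.

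Withdrawing the tests is therefore reasonable.

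**The time summary.** An invented example shows the worst case. Arm A has movements at 1 and 2 h and three patients with none by 24 h. Arm B has movements at 1, 2, 4, 8 and 20 h.
- Mean of recorded times: A (1 + 2)/2 = 1.5 h; B (1 + 2 + 4 + 8 + 20)/5 = 7.0 h. A looks faster.
- Median over all five: A is not reached by 24 h; B is 4 h. B is faster.

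The reversal needs a mean of recorded times. Neither document says one was used, and the SAP does not say that the withdrawn ANOVA was meant for this outcome.

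**The case for a change.** The best case for a change is that this SAP is the later document, is written in the past tense, and already explains the loss of participants, so it is the natural place to state what sample remained. Even if counts belong in the results, the revised goal and the choice of summaries are planning content. With a handful of patients per arm, the choice of time summary could reverse the apparent ordering on a listed outcome, and one short note would settle it.

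The description of what is missing stands, and the handling of patients without a bowel movement by 24 hours is its most substantive part. It does not amount to a fault in the plan. No stated rule would give a wrong result, and a Kaplan-Meier estimate or a listing would replace no stated method. Numbers analysed per arm normally appear with the results. The past tense also works against the request: the analyses had been done by the SAP's date, so a note added now would record choices and could not prespecify them. Marking 60 as pre-study, 5 per month as predicted and the analysis as descriptive would repeat what the SAP already says.

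**Conclusion.** No change to the plan follows. The SAP omits the goal of 15, the per-arm numbers and the names of its summaries, but it contains no wrong figure on this point and no contradiction with the protocol. Read together, the two documents disclose the original size, the reduction and the withdrawal of all tests. A comparative aim addressed only descriptively is a limitation that the SAP states openly.

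No test result or decision depends on the gap, and an analyst can fill it sensibly: responders over patients treated in each arm, and individual times listed with the number who had none. The figures of 5 per arm, 15% to 95% and 39% assume that 15 patients were reached and split evenly; the 39% also assumes conventional alpha and power. The time example is invented. The documents report no results, so none of these describes what was observed.

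### Does the SAP's investigator-blinding statement need changing, given that the three arms differ visibly by route and tablet count?

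*SAP*

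**What the plan says.** Under Feasibility, the SAP has two statements on allocation and masking. Participants are randomised 1:1:1, with pharmacy staff making the assignment, and "Study investigators blinded to randomization and study drug". It names nobody else as blinded.

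The protocol mentions neither randomisation nor blinding. Study Procedure 1.a says only that patients "will be screened for inclusion in one of three groups". The groups are oral methylnaltrexone, "Methylnaltrexone 12mg subcutaneous injection" and oral naloxegol. Patients are "offered inclusion in the study by one of the Emergency Department faculty" (section 4.a).

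On outcomes, the Purpose section states: "The secondary outcome of this study is the time to effectiveness of subcutaneous versus oral therapy". Patients without a bowel movement by 3 hours are to "be contacted in 24 hours to record the time of any successful bowel movements" after that point (section 1.c.ii). Item 2.i of the data list is "Side effects noted by patient or staff".

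Under Statistical considerations, the SAP says the pool of potential participants shrank until continuing was not feasible, and that therefore "only descriptive statistics were performed".

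**The concern.** A blinding claim normally needs a mechanism, and none is given here. An injection cannot be mistaken for tablets, and the two oral regimens appear to differ in tablet count. The secondary outcome compares subcutaneous with oral therapy, which is the difference that a patient or a nurse can see.

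The exposed data are also the sort that knowledge of treatment can colour: late bowel movement times obtained by contacting the patient, and side effects noticed by patients or staff. The documents do not say who gave the dose, who recorded events in the first 3 hours, who made the 24-hour contact, or whether the faculty who offered enrolment were among the blinded investigators. A report that repeated the SAP sentence without qualification could suggest more protection against bias than the documents support.

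**Working it through.** **1. Can the arms be told apart?** The inputs come from the protocol's Estimated Budget.

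- Oral methylnaltrexone: $51.21 per dose at $17.07 per tablet, so 51.21 / 17.07 = 3 tablets.
- Naloxegol: $9.14 per dose at $9.14 per tablet, so 9.14 / 9.14 = 1 tablet.
- Subcutaneous methylnaltrexone: 1 injection at $93.96.

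The protocol's total reproduces: 20 × 51.21 + 20 × 93.96 + 20 × 9.14 = 1,024.20 + 1,879.20 + 182.80 = $3,086.20.

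The tablet counts are inferred from prices. The arm descriptions give total milligrams only, and the naloxegol arm is worded in the plural, although the budget lists a 25 mg tablet against a 25 mg total. The difference in route needs no inference, and route alone matters for the secondary outcome. The budget prices active drug only, and neither document mentions a placebo, sham injection or dummy.

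**2. Who is claimed to be blinded, and who could see the arm?**

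| Role | Blinding claimed? | Could the arm be seen, as described? |
|---|---|---|
| Pharmacy staff | No | Yes, they assign it |
| Patient | No | Yes |
| Person giving or observing the dose | No | Yes |
| Study investigators | Yes | Only if they see dosing or learn the arm while collecting data; not stated |

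The claim and the visible differences meet only in the last row, and there the documents are silent. They do not contradict each other.

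**3. Which data are exposed?** Of the 9 listed items (2.a to 2.i), 2 are measured after dosing: time to bowel movement (2.g) and side effects (2.i). Neither has a stated masked recorder.

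**4. What would rewording change?** The protocol's enrolment goal is 15, which is 15 / 3 = 5 per arm if the split is even, against 60 in the original sample size (3 × 14 + 18 = 60). The Chi-Square and ANOVA comparisons appear in the SAP only as the previous plan. The SAP, dated 09/04/2024, describes the descriptive analysis as already done. No p-value, interval or decision rule depends on the blinding sentence. Rewording it would leave every tabulated value as it is.

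**The case for a change.** The strongest reply is that descriptive results are not immune. A listed time or a side-effect count is still shaped by who knew the arm. With so few patients and no tests, readers have little to go on beyond the description of the design, so that description should be accurate. The remedy is cheap, since it is only wording.

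Part of this stands. The documents do leave open who dosed, who recorded and who knew, and a results report should say so by role. But that is a matter of reporting what happened, and the plan cannot supply it after the event.

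The obvious replacement text, calling the trial open-label to patients and dosing staff, would assert something the documents do not establish, because silence about a dummy does not prove there was none. It could also displace an investigator-blinding statement that may be true. Advice on masking future participants has little evident use once continuation has been found infeasible. The absence of randomisation from the protocol is a separate gap; the SAP already states it, and adding it to the protocol now would not alter conduct.

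**Conclusion.** No change to the plan. The observation is accurate as far as it goes: as described, masking does not reach patients or anyone giving or seeing the dose, and the mechanism for investigators is not set out. The SAP sentence is limited to study investigators and is not shown to be wrong. This is missing detail that whoever reports the trial can fill from what was actually done.

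The reach is small: 2 of 9 data items, an enrolment goal of 15, and no inferential test. The size and direction of any bias cannot be derived.

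The conclusion rests on three readings: that enrolment has ended, as the SAP's past tense indicates; that nothing beyond descriptive statistics will be presented; and that the blinding sentence is taken to cover investigators only. If a report extended it to patients or treating staff, that report would be open to criticism, but the plan would not be at fault.

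### Does the SAP need a rule for patients with no recorded bowel-movement time?

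*SAP*

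**What the plan says.** The SAP's Statistical considerations record that chi-square tests and ANOVA had been planned, that recruitment became infeasible, and the outcome of that: "Therefore, only descriptive statistics were performed. No conclusive tests were performed". There is no analysis set, no denominator and no rule for absent times. The SAP's sample-size paragraph describes the pre-study calculation for 60, "adding 18 participants to account for dropouts". Allocation is described as "Participants randomized in a 1:1:1 pattern assigned by pharmacy staff".

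The protocol (Study Procedure, 1.c) has two paths. One patient will "Have a successful bowel movement, thus completing their time in the study to continue with standard patient care". The other will "Not have a successful bowel movement after 3 hours, continue with standard patient care, and be contacted in 24 hours", the purpose of the contact being to "record the time of any successful bowel movements after the 3 hours study period". Under Treatment of subjects, "Patient follow-up will cease after 24 hours". The outcome item in the data list (2.g) is "Time to successful bowel movement after treatment". The protocol's Feasibility section gives a reduced goal of 15 patients. Its secondary outcome is time to effectiveness, subcutaneous against oral.

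**The concern.** A proportion needs a denominator, and a mean time needs a rule for patients who have no time. The SAP supplies neither, and with no tests performed the descriptive summaries are the whole result.

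The follow-up scheme sharpens the worry. Early responders are finished and their time is known. Everyone else depends on a later contact, so failed contacts fall only on slower patients. A patient who is reached but has had no movement has no event time either. If recorded times were averaged and the rest dropped, each arm would look faster than it was, and the comparison between routes could be shrunk, hidden or reversed. The planning figures also allowed for sizeable dropout. With about five patients per arm, one patient is 20 percentage points of an arm's response.

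Times after 3 hours also reflect standard care given after the study drug, and the documents do not say which effect is meant.

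**Working it through.** **1. The dropout allowance.** Inputs from the SAP: 14 per arm, three arms, 18 added, total 60.

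- 3 × 14 = 42; 42 + 18 = 60 = 3 × 20. The stated total is reproduced.
- 18/60 = 30%, and 42/(1 − 0.30) = 60. The SAP does not print the 30%; it is derived.
- The allowance belongs to the plan for 60. No rate is restated for the goal of 15, and dropout is not defined as failed 24-hour contact. It is not evidence of actual loss.

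**2. What is known for each kind of patient** (protocol, Study Procedure 1.c):

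| Patient | 3-hour status | 24-hour status | Time |
|---|---|---|---|
| Movement within 3 h | response | response | known |
| None at 3 h, reached, later movement | non-response | response | known |
| None at 3 h, reached, still none | non-response | non-response | beyond 24 h |
| None at 3 h, not reached | non-response | unknown | beyond 3 h |
| Left before 3 h (not covered in the documents) | unknown | unknown | unknown |

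**3. Response at 3 hours.** Assume 5 per arm (15 split equally) with 2 responders by 3 hours. Over all patients this is 2/5 = 40%. Leaving out one or two unreached patients gives 2/4 = 50% or 2/3 = 67%. By the fourth row of the table, those patients were already observed as non-responders, so the higher figures arise only if an observed outcome is discarded.

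**4. Response at 24 hours.** Here the unreached patient is truly unknown. Each one leaves 1/5 = 20 points open. With 2 of 5 known responders, the range is 40% to 60% with one unreached and 40% to 80% with two.

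**5. Time to bowel movement.** Assume exponential times with median *m*, no effect of standard care, and follow-up to 24 h. Let *r* = ln 2/*m*, so the fraction with none by 24 h is 2^(−24/*m*).

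- Restricted mean to 24 h = (1/*r*)(1 − 2^(−24/*m*)).
- Mean of recorded times only = 1/*r* − 24·2^(−24/*m*)/(1 − 2^(−24/*m*)).

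| Median | 1/*r* | None by 24 h | Restricted mean | Recorded-only mean |
|---|---|---|---|---|
| 2 h | 2.89 | 0.0% | 2.88 | 2.88 |
| 6 h | 8.66 | 6.2% | 8.12 | 7.06 |
| 12 h | 17.31 | 25% | 12.98 | 9.31 |

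The gap for 6 against 12 h is 4.87 h restricted and 2.26 h recorded-only. For 2 against 6 h it is 5.23 h and 4.18 h (differences taken before rounding). The restricted mean is the fair comparator because follow-up ends at 24 h. Against the unrestricted gaps (17.31 − 8.66, about 8.66 h before rounding, and 8.66 − 2.89 = 5.77 h), part of the shrinkage comes from that horizon, which no counting rule alters.

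**6. Whether ordinary reporting shows the problem.** Take invented arms of five. A has times 1, 2, 8, 13 h and one with none; B has 2, 10 h and three with none. Recorded means are (1+2+8+13)/4 = 6.0 and (2+10)/2 = 6.0, which look equal. The counts are 4/5 and 2/5. With patients without a movement ranked last, the medians are 8 h and not reached by 24 h. Printing the counts or the ten individual outcomes removes the illusion.

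**The case for a change.** The strongest case for a change is that being descriptive is no protection. The summaries are the only results, time to effectiveness is a named outcome, and the documents do not fix 3 hours as the window for the primary outcome. The data list has a single time item, and nothing in it separates a patient with no movement by 24 hours from one who was not reached. The harm is also not confined to arms that differ in response: unequal contact rates could bias the comparison of times even if response were the same.

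Much of this stands. The rule is absent, the link between loss and slow response is built into the follow-up, and a bare mean of recorded times would be too short within an arm. Three parts do not carry the weight put on them. The data list is a set of headings, not the case report form, and a contact made to ask about later movements would naturally yield a time or a report of none. The 30% describes a plan no longer in force. The invented arms show that distortion is possible, not that it is likely.

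**Conclusion.** The omission is real, but it is missing detail and not a faulty method. No rule stated in the SAP gives a wrong answer. An analyst describing about 15 patients would sensibly count over everyone randomised, keep unreached patients as 3-hour non-responders, and show the times one by one. Times after 3 hours are valid for assignment plus later standard care, and calling them that is a matter of labelling.

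The SAP is dated 09/04/2024 and written in the past tense, so a rule added now would not be prespecification. No test, alpha or power is affected. If recorded times alone were averaged, the assumed cases show a gap of 4.87 h appearing as 2.26 h, or 5.23 h as 4.18 h. Whether that happened, and how many patients were unreached, cannot be told from the documents.

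The conclusion rests on patients being observed to 3 hours as the protocol describes. The figures rest on the assumed exponential times and, for the percentages, on 5 per arm. The number actually enrolled is not given. A reader of the results should look for counts by 3 h, by 24 h, none and not reached, but the plan needs no change.
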